2.4.4 Secondary effectiveness analysis

- *Percentage of responders as measured by the Blinded Evaluator at 3, 9 and 12 months after last treatment in Treatment group and at 3 months after randomization as well as 3, 6, 9 and 12 months after last treatment for control group*

The percentage of responders will be calculated at each time point and analyzed descriptively. At 3 months after last treatment for Treatment group and after randomization for Control group Fishers' Exact test will be used to compare the responder rates.

- *Percentage of responders as assessed by the Treating Investigator at each follow-up visit*

The percentage of responders will be calculated at each time point. At Week 4, Month 3 and Month 6 after last treatment for Treatment group and after randomization for Control group Fishers' Exact test will be used to compare the responder rates.

CC1

2.5 Safety Analysis

All safety variables will be summarized descriptively based on the safety population.

2.5.1 Extent of exposure

Data of extent of exposure and treatment procedure will be summarized in total and by group, for initial treatment and touch-up separately. Injection volume will be summarized by group for initial treatment and touch-up separately. Other relevant injection parameters, such as injection depth, injection method will be presented in a similar way

2.5.2 Adverse events

All AEs will be coded according to MedDRA. All AE summaries below will be presented by treatment.

An overall summary of AEs will be presented. The summary will include the total number of events, frequency counts and percentages of subjects with

- Any AEs and SAEs reported
- Any AEs and SAEs related to product and/or injection procedure
- Unrelated AEs and SAEs
- No AEs reported

Summaries of related AEs after each treatment occasion (including the total number of events, number and percentage of subjects) will be displayed by system organ class (SOC), preferred term

	Title Statistical Analysis Plan 43CH1627 - Chin	Doc id MA-38115
--	---	---------------------------

Effective date: 2018-08-23 03:02

Effective

Version: 1.0

(PT) and intensity. The duration and number of days to onset of related AEs will be summarized by SOC and PT using mean, SD, minimum, maximum, and median statistics.

Time to onset of an AE will be derived as the start date minus the date of most recent treatment. If the start date is missing, it will be assumed that the AE started on the day of most recent treatment.

Duration of an AE will be derived as the stop date minus the start date + 1. If the start date is missing, it will be assumed that the AE started on the day of most recent treatment. Missing stop date will not be imputed and therefore no duration will be calculated in these cases. Instead, the number of AEs that were ongoing at the end of the study will be given.

CCI

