8.4.3 Recording Instructions

AE will begin to be collected after ICF signed. Each subject will be questioned about AEs at each clinical visit following the screening visit. The question asked will be "Since your last clinical visit have you had any health problems?" Information on AEs can also be obtained from signs and symptoms detected during each examination or from a laboratory test, observations by the study personnel, **CCI** [REDACTED] spontaneous reports from the subjects.

When an AE is related to a device deficiency (refer to section 8.5), including technical device malfunction, the AE shall be recorded on the AE module in the eCRF and the technical complaint shall be reported separately on the clinical study complaint form.

Investigators, or other study personnel, will record all AEs in the eCRF, including:

| | | |
|--|--|---------------------------|
|  GALDERMA | Title 43CH1627 Clinical Study Protocol | Doc id MA-34970 |
|--|--|---------------------------|

2018-01-15 10:39

Effective date:

- Event term (recorded in standard medical terminology and avoiding abbreviations),
- Description of event and affected area (if applicable),
- Start date (First day with symptoms)
- Stop date (Last day with symptoms)
- Intensity (mild, moderate or severe according to definition in section 8.4.3.1)
- Seriousness (serious or not serious, according to definition in section 8.4.2)
- Causal relationship to study product and study product injection procedure (yes or no)
- Action taken (none, medication treatment, non-pharmacological treatment or other procedures/ tests, subject withdrawn)
- Outcome of the AE (ongoing, recovered, recovered with sequelae, death, chronic/ stable, not recovered at study end)

The AE module in the eCRF must be signed and dated by the Investigator.

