9.2.1 Data entry

All data shall be entered in English. The eCRFs should always reflect the latest observations on the subjects participating in the study. Therefore, the eCRFs shall be completed within 5 working days after the subject's visit. The subject's identity must always remain confidential, i.e. the name and address of the subjects must not be registered in the eCRFs or in the database. The Investigator must verify that all data entries in the eCRFs are accurate and correct. If some assessments are not done, or if certain information is not available, not applicable or unknown, the Investigator shall indicate this in the eCRF. The Investigator shall electronically sign off the study data. By signing, the Investigator takes responsibility for the accuracy, completeness, and legibility of the data reported to the Sponsor in the eCRF.

| | | |
|--|--|---------------------------|
|  GALDERMA | Title 43CH1627 Clinical Study Protocol | Doc id MA-34970 |
|--|--|---------------------------|

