1.2.3 Safety objectives

The safety objectives are:

- Incidence, intensity, duration and onset of adverse events (AEs) collected throughout the study

CCI

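### A missing AE start date is always set to the most recent injection, which misstates onset and duration for related events first reported at later follow-up visits

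*SAP*

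**What the plan says.** SAP 2.5.2 gives the same rule under time to onset and again under duration: "If the start date is missing, it will be assumed that the AE started on the day of most recent treatment". The two derivations are:

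- "Time to onset of an AE will be derived as the start date minus the date of most recent treatment"
- "Duration of an AE will be derived as the stop date minus the start date + 1"

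Stop dates are treated differently: "Missing stop date will not be imputed and therefore no duration will be calculated in these cases". The results feed Tables A 44 and A 45: "The duration and number of days to onset of related AEs will be summarized by SOC and PT using mean, SD, minimum, maximum, and median".

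SAP 1.2.3 lists as a safety objective: "Incidence, intensity, duration and onset of adverse events (AEs) collected throughout the study". SAP 1.6 narrows the endpoint to related events.

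Protocol 8.4.3 has subjects asked about AEs at each clinical visit after screening, with this question: "Since your last clinical visit have you had any health problems". The start date is one of the AE items it lists for the eCRF. Protocol 9.2.1 allows for gaps: "if certain information is not available, not applicable or unknown, the Investigator shall indicate this in the eCRF". Protocol 4.7 places follow-up visits at 4 weeks and at 3, 6, 9 and 12 months after last treatment in both groups.

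**The concern.** Onset is measured from the most recent treatment, so an event imputed to that day has onset 0 whatever happened. Any real delay before the event began is then added to its duration, day for day. The recall period of the AE question usually gives a much closer lower limit for the start, namely the preceding visit, and the rule does not use it.

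The error has a direction. Protocol 8.4.8 describes the expected injection reactions as typically starting on the treatment day and resolving within a week. Setting every unknown start to the treatment day moves a late event into that onset pattern and also gives it a duration that may be months too long. Onset and duration are named safety endpoints, and with summaries by preferred term a single event can move a mean, an SD or a maximum.

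**Working it through.** The plan gives no onset or duration figure to reproduce, so the check applies the SAP formulas to the visit schedule.

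**Inputs.** Visits after last treatment, from Protocol 4.7: 4 weeks ±3 days, 3 and 6 months ±1 week, 9 and 12 months ±2 weeks. Assumption: one month is 30.44 days, so the nominal visit days are 28, 91, 183, 274 and 365.

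**Step 1: size of the error.** Imputed start = day 0, so the onset error is the true onset day. Duration = stop − start + 1, so a recorded stop date makes the duration too long by the same number of days. If the event began between the preceding visit and the reporting visit, the error lies between the earliest day of the first and the latest day of the second.

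| First reported at | Earliest preceding visit | Latest reporting visit | Error, days |
|---|---|---|---|
| 4W | 0 (treatment) | 28 + 3 = 31 | 0–31 |
| 3M | 28 − 3 = 25 | 91 + 7 = 98 | 25–98 |
| 6M | 91 − 7 = 84 | 183 + 7 = 190 | 84–190 |
| 9M | 183 − 7 = 176 | 274 + 14 = 288 | 176–288 |
| 12M | 274 − 14 = 260 | 365 + 14 = 379 | 260–379 |

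From Month 6 on, the error runs from 84/30.44 = 2.8 months to 379/30.44 = 12.5 months.

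**Step 2: one event.** Assume a related event that truly lasts 7 days, stops the day before the reporting visit, and has a stop date but no start date. The last column sets the start to the nominal preceding visit.

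| First reported at | Stop day | True onset | SAP duration | Duration from preceding visit |
|---|---|---|---|---|
| 3M | 90 | 84 | 90 − 0 + 1 = 91 | 90 − 28 + 1 = 63 |
| 6M | 182 | 176 | 182 − 0 + 1 = 183 | 182 − 91 + 1 = 92 |
| 9M | 273 | 267 | 273 − 0 + 1 = 274 | 273 − 183 + 1 = 91 |
| 12M | 364 | 358 | 364 − 0 + 1 = 365 | 364 − 274 + 1 = 91 |

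The SAP onset is 0 in every row. With the preceding-visit date it is 28, 91, 183 and 274.

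**Step 3: effect on a summary.** Assume 20 related events of 5 days in one preferred term, plus the Month 12 event above.

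- True mean duration: (100 + 7)/21 = 5.1 days.
- SAP rule: (100 + 365)/21 = 22.1 days, maximum 365.
- Start at the preceding visit: (100 + 91)/21 = 9.1 days, maximum 91.
- Median: 5 days in all three.

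With 100 such 5-day events instead of 20, the means are (500 + 7)/101 = 5.0, (500 + 365)/101 = 8.6 and (500 + 91)/101 = 5.9 days.

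**The case against.** The case for leaving the rule alone has real substance.

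- **The rule is right where most events lie.** Injection reactions typically start on the treatment day. A blanket rule that started every undated event at the preceding visit would misdate reactions recorded at their own treatment visit. In the Control Group, a reaction recorded at the Month 6 treatment visit would be dated to Month 3, before any product was given. This stands, and the fix must allow for it.
- **The situation should be rare.** The start date is a listed eCRF item, the investigator signs the AE module, and Protocol 9.2.2 provides full review of the eCRFs with queries. Duration is inflated only when the start is missing and the stop is known. This stands.
- **The consequence is narrow.** Two descriptive tables are affected, and the median is also reported. Incidence, intensity, causality and effectiveness results do not change. This stands.
- **The lower limit is inferred.** A reader might conclude that an event first reported at Month 9 must have begun after the Month 6 visit. The documents do not go that far: a visit can be missed, an event can go unnoticed, and AEs also come from examinations, laboratory tests and spontaneous reports.
- **Two stronger readings are not supported.** A reader might infer that partial dates are thrown away, or that an event reported before a touch-up injection would be dated to that injection. The SAP does not say that a partial date counts as missing. The natural sense of most recent treatment is the one before the event. Both are ambiguities worth a clause, not errors.

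Some SAP text after the rule is blacked out, so nothing is inferred from it either way.

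What the objection does not remove is that, for later first reports, the visible rule assigns a value that the protocol's own visit-by-visit questioning makes implausible.

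**Conclusion.** The point holds as a minor one. For a related AE with no start date, first reported after the first post-injection visit, SAP 2.5.2 gives onset 0. When a stop date exists, it overstates duration by roughly one to three months at Month 3 and by about three to twelve months from Month 6 on. For an ongoing event only the onset is wrong.

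The size rests on attendance at the preceding visit, on the event not having been overlooked there, and on nominal month lengths. The number of missing start dates cannot be known from the documents and is probably small. The damage falls on means, SDs and maxima in Tables A 44 and A 45; medians move little.

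A reader might infer that the safety profile as a whole would be distorted or that delayed reactions would be systematically hidden. The documents do not support that, because the counts of events and of subjects affected stay the same and most events should carry a recorded start date.

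**What to change.** Amend SAP 2.5.2 as follows:

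- Keep the treatment-day rule for AEs recorded after the injection at a treatment visit, or first reported at the first attended visit after a treatment. Define the treatment as the last one given before the event was reported.
- For AEs first reported at a later visit, set a missing start to the date of the preceding attended visit, and never later than the stop date.
- Keep any known month or year of a partial date.
- Flag imputed dates, and repeat Tables A 44 and A 45 without them.

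The cost is some SAP wording and a little programming. The AE items in Protocol 8.4.3 do not include the visit of first report, so it would have to be derived. Comparing entry dates with visit dates is one route, but an approximate one, since Protocol 9.2.1 allows five working days for eCRF completion. The new rule is still an earliest-date imputation and can overstate duration by up to one visit interval, as the 91 days for a 7-day event show. That is why the repeat without imputed dates is needed.

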3.2 Endpoints of the study

3.2.1 Primary effectiveness endpoint:

- Percentage of responders, defined by at least 1 point improvement from baseline on the Galderma Chin Retrusion Scale (GCRS), as measured by the Blinded Evaluator at 6 months (after last treatment in Treatment Group, and after randomization in Control Group).

3.2.2 Secondary effectiveness endpoints:

- Percentage of responders, defined by at least 1 point improvement from baseline on the GCRS, as measured by the Blinded Evaluator at 3, 9 and 12 months after last treatment in Treatment Group, and at 3 months after randomization, as well as 3, 6, 9 and 12 months after the last treatment in Control Group.
- Percentage of responders, defined by at least 1 point improvement from baseline on the GCRS, as measured by the Treating Investigator at each follow up visit.

CCI

3.2.3 Safety endpoints:

- Incidence, intensity, duration, and onset of adverse events (AEs) collected throughout the study.

CCI

4 Design of the Study

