The SAE form (CFDA template in Chinese) must be signed and dated by the Investigator. If the initial 24-hour SAE report does not contain full information or if it is made without using the SAE form, the fully completed and signed SAE form shall be e-mailed or faxed to the Sponsor (contact details refer to 24-hour contact person list in ISF). A copy of the fully completed SAE form shall be kept at the site.

In addition, according to national regulations, the investigator will report a SAE Form (CFDA SAE template) to the administrative department of medical device clinical trials in his/her hospital, and they should, within 24 hours, deliver a written report to the corresponding Ethics Committee and the local food and drug administrative department of province, autonomous region and municipality at the place where the clinical trial institution locates. In case of a death incident, the clinical trial institutions and investigators should furnish the Ethics Committee and the Sponsor Representative with all required materials.

The Sponsor Representative in China is responsible for, within five (5) business days upon being informed, reporting any SAE or device defect with the likelihood of SAE to Shanghai Municipal FDA and Shanghai Municipal Commission of Health and Family Planning by fax or mail. The relevant correspondence will be documented in TMF; meanwhile, the Sponsor Representative should notify other clinical trial institutions and investigators participating in the study, and promptly report it to the Ethics Committee of the involved clinical trial institutions via the administrative department of medical device clinical trials according to national regulations.

8.4.6 Follow-up of Unresolved Events after study termination and new Events after study termination.

All serious as well as non-serious AEs with a causal relationship to the study product or treatment procedure and ongoing at study end, shall be followed up after the subject's

| | | |
|--|---|-----------------------------------|
|  | 
Title 43CH1627 Clinical Study Protocol
 | 
Doc id MA-34970
 |
|--|---|-----------------------------------|

2018-01-15 10:39

Effective date:

Effective

Version: 3.0

participation in the study is over. Such events shall be followed-up after the last study visit until resolved, assessed as chronic or stable, or for at least three months. Final outcome after study end should be reported on a paper AE form.

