1.6 Safety endpoints

Safety endpoints include:

(v) Incidence, intensity, duration, and onset of related Adverse Events (AEs) collected throughout the whole study

 GALDERMA	<small>Title</small> Statistical Analysis Plan 43CH1627 - Chin	<small>Doc id</small> MA-38115
---	--	--

CCI

Effective date: 2018-08-23 03:02

Effective

Version: 1.0

 Title **Statistical Analysis Plan 43CH1627 - Chin** Doc id **MA-38115**

Effective date: 2018-08-23 03:02

Effective

Version: 1.0

2 Statistical Methods

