**Table A 42. All AEs by MedDRA System Organ Class, Preferred Term and intensity (Safety)**

		No treatment at baseline N=xx		Treatment with Restylane Defyne N=xx	
		Events	Subjects	Events #	Subjects n (%)
Primary System Organ Class Preferred Term	Intensity	Events	Subjects	Events #	Subjects n (%)
Any AE	Total	xx	xx (xx.x)	xx	xx (xx.x)
	Mild	xx	xx (xx.x)	xx	xx (xx.x)
	Moderate	xx	xx (xx.x)	xx	xx (xx.x)
	Severe	xx	xx (xx.x)	xx	xx (xx.x)
SOC1	Total	xx	xx (xx.x)	xx	xx (xx.x)
	Mild	xx	xx (xx.x)	xx	xx (xx.x)
	Moderate	xx	xx (xx.x)	xx	xx (xx.x)
	Severe	xx	xx (xx.x)	xx	xx (xx.x)
PT11	Total	xx	xx (xx.x)	xx	xx (xx.x)
	Mild	xx	xx (xx.x)	xx	xx (xx.x)
	Moderate	xx	xx (xx.x)	xx	xx (xx.x)
	Severe	xx	xx (xx.x)	xx	xx (xx.x)

Table A 43. Related AEs by MedDRA System Organ Class, Preferred Term and intensity (Safety)

		Treatment with Restylane Defyne N=xx	
Primary System Organ Class Preferred Term	Intensity	Events #	Subjects n (%)
Any related AE	Total	xx	xx (xx.x)
	Mild	xx	xx (xx.x)
	Moderate	xx	xx (xx.x)
	Severe	xx	xx (xx.x)
SOC1	Total	xx	xx (xx.x)
	Mild	xx	xx (xx.x)
	Moderate	xx	xx (xx.x)
	Severe	xx	xx (xx.x)
PT11	Total	xx	xx (xx.x)
	Mild	xx	xx (xx.x)
	Moderate	xx	xx (xx.x)
	Severe	xx	xx (xx.x)

Note: Treatment with Restylane Defyne columns include data from subjects in the Restylane Defyne group after their initial treatment at baseline, as well as data from subjects in the Control group after their initial treatment at Month 6 after randomization

Note: At each level of summarization subjects are counted once

% = 100*n/N

Table A 44. Duration (days) of related AEs by MedDRA System Organ Class and Preferred Term (safety)

	Treatment with Restylane Defyne N=xx						
	Ongoing	n	mean	SD	min	Median	Max
Any related AE							
SOC1							
PT11							
PT12							

Note: Treatment with Restylane Defyne columns include data from subjects in the Restylane Defyne group after their initial treatment at baseline, as well as data from subjects in the Control group after their initial treatment at Month 6 after randomization

Table A 45. Time to onset (days) of related AEs, by MedDRA System Organ Class and Preferred Term (Safety)

As Table A 44.

Note: Treatment with Restylane Defyne columns include data from subjects in the Restylane Defyne group after their initial treatment at baseline, as well as data from subjects in the Control group after their initial treatment at Month 6 after randomization

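### Table A 44 summarises AE duration over resolved events only, so mean and maximum are too low when long-lasting events are still ongoing, and the median suffers mainly in terms with many ongoing events

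*SAP*

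**What the plan says.** Protocol 3.2.3 lists as a safety endpoint: "Incidence, intensity, duration, and onset of adverse events (AEs) collected throughout the study". SAP 1.6 narrows this to related events: "Incidence, intensity, duration, and onset of related Adverse Events (AEs) collected throughout the whole study".

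SAP 2.5.2 gives the derivation: "Duration of an AE will be derived as the stop date minus the start date + 1". A missing start date is set to the day of the most recent treatment. For a missing stop date the rule differs: "Missing stop date will not be imputed and therefore no duration will be calculated in these cases". The next sentence says what is shown in place of a duration: "Instead, the number of AEs that were ongoing at the end of the study will be given".

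The summary is specified as follows: "The duration and number of days to onset of related AEs will be summarized by SOC and PT using mean, SD, minimum, maximum, and median". Protocol 10.5 plans the same statistics. The output is "Table A 44. Duration (days) of related AEs by MedDRA System Organ Class and Preferred Term", whose columns are Ongoing, n, mean, SD, min, median and max.

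Protocol 8.4.6 requires related events that are open at study end to be followed until they resolve or are judged chronic or stable, or for at least three months. It adds: "Final outcome after study end should be reported on a paper AE form". The visible SAP text does not say whether those later dates enter Table A 44.

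**The concern.** An event still open at last contact is a right-censored duration: it has lasted at least as long as observed. At a given onset date, the longer an event lasts, the more likely it is to be open at the end and so to receive no duration. Averaging the resolved events alone favours short ones. The reported maximum can even be shorter than the time for which an ongoing event has already been observed.

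Common injection reactions are expected to resolve within a week (Protocol 2.6 and 8.4.8), so they are barely touched. Protocol 2.6 also names palpable lumps, gel displacement and inflammation. If such an event persists, its row would understate how long it lasts, in a study meant to support registration (Protocol 2.5). The interim analysis could leave more events open, because Control subjects need only have reached 6 months after last treatment.

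**Working it through.** **Inputs.** The documents supply the derivation, the stop-date rule and the statistics (SAP 2.5.2, Table A 44), the 12-month final visit after last treatment (Protocol 4.7), and the one-week expectation for common reactions. They give no number of related AEs, no share ongoing and no duration for persistent events. There is thus no stated figure to reproduce, and every number below rests on assumed inputs.

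**Step 1: simple arithmetic.** Take 100 related events. Resolved events average 5 days; k events are ongoing and each has been observed for L days. The SAP rule reports 5.0 whatever k is. Counting each ongoing event at its observed minimum gives ((100 − k) × 5 + k × L)/100:

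| k | L = 30 | L = 365 |
|---|---|---|
| 0 | 5.0 | 5.0 |
| 1 | 5.25 | 8.6 |
| 5 | 6.25 | 23.0 |
| 10 | 7.5 | 41.0 |

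**Step 2: mean under a mixture.** Follow-up is 365 days. Short events last 1 day plus an exponential with mean 6 (mean 7), start on the treatment day, and in effect all resolve. A share of 5% are long: 1 day plus an exponential with mean 180 (mean 181).

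- True overall mean: 0.95 × 7 + 0.05 × 181 = 15.7 days.
- Long events starting on the treatment day: exp(−364/180) = 0.1324, so 0.8676 resolve. Their mean is 181 − 364 × 0.1324/0.8676, about 125 days. Reported overall mean: (0.95 × 7 + 0.05 × 0.8676 × 125.47)/(0.95 + 0.05 × 0.8676) = 12.2 days.
- Long events starting uniformly over follow-up: (364 − 180 × 0.8676)/365 = 0.569 resolve, so about 43% are ongoing. The mean of those resolved is about 87 days (integrating over onset: 1 + 17,969/207.8 = 87.5). Reported overall mean: (0.95 × 7 + 0.05 × 0.569 × 87.5)/(0.95 + 0.05 × 0.569) = 9.3 days.

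With uniform onset, other choices of share and mean run from 8.7 true against 7.9 reported (2% long, mean 90 days) to 77.6 against 15.1 (20% long, mean 360 days).

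**Step 3: median.** In the same 5% model, the overall median is 5.5 days true and 5.3 reported with uniform onset. For the long-lasting term alone, the true median is 1 + 180 × ln 2 = 126 days. It is reported as 103 with treatment-day onset and 69 with uniform onset.

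A second simulation used lognormal short reactions (median 4 days) and persistent events with mean 180 or 365 days:

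| Persistent share | Ongoing | Median reported | Median true |
|---|---|---|---|
| up to 20% | up to 13% | equal to the true value | 4–5 |
| 50% | 7–32% | 6–9 | 11–13 |
| 80% | 11–50% | 23–78 | 85–173 |

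**Step 4: does a censoring-aware estimate recover the truth?** With ongoing events censored at last contact, the Kaplan-Meier median for the long-lasting term is 126 days against a true 126. In the second simulation it is within 1 day of the truth in every setting.

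**The case against.** The strongest reply is that the SAP is open about the exclusion. It says that ongoing events will be counted, and Table A 44 prints that count beside n for each SOC and preferred term. A reader might infer that ongoing events vanish from the safety report; the documents do not support that. The AE tables by intensity (A 42 and A 43) are not restricted to events with a stop date. In a term with 43% of events ongoing, the count would warn the reader. This stands, but a count does not separate an event open for 10 days from one open for 300.

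A reader might also infer that the median is biased in general. It is not: the overall median hardly moves, and the SAP already reports it. The problem is confined to terms with a large share of ongoing events.

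Nor are the excluded events always the longest. One that began just before the last visit may be short, and a resolved event may simply lack a recorded stop date; the SAP does not separate these cases.

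Finally, the reader should not conclude that post-study outcomes are discarded. The visible SAP is silent, redacted text follows directly in 2.5.2, and the endpoint concerns events collected during the study. Whether to use later dates is a choice to be stated. Kaplan-Meier estimates will also be uninformative for terms with very few events.

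**Conclusion.** The point holds for the mean and maximum whenever long-lasting events are open at last contact, and for the median in preferred terms with many ongoing events. The direction follows from the rule itself. The size cannot be established, because it depends on an ongoing fraction that the documents do not give. The figures above also assume exponential long events and 365 days of follow-up, and onset timing alone moves the reported overall mean between 9.3 and 12.2 days. If nothing is ongoing, Table A 44 is correct as planned.

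A reader might infer that the safety conclusions or the trial result are compromised. That does not follow: the safety analysis is descriptive (SAP 2.5), and duration enters no test or success criterion. This is an inexpensive improvement to how a named safety endpoint is reported.

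**What to change.** In SAP 2.5.2 and Table A 44:

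- Keep the Ongoing count, and label mean, SD, min, median and max as resolved events only.
- Add a Kaplan-Meier median by preferred term, with quartiles where estimable, censoring ongoing events at last contact.
- For terms with too few events, list the observed minimum duration of each ongoing event instead.
- Distinguish events that are ongoing from resolved events whose stop date is missing.
- State whether stop dates from the post-study paper AE form are used.

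The cost is SAP wording and one extra descriptive summary from dates already collected, plus entry of a few paper-form dates if the sponsor chooses to use them. The added estimates will be unstable for sparse terms and assume that censoring is unrelated to how long an event would have lasted. Reported durations may look longer. The primary analysis does not change.
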